## 7.0 RANDOMIZATION/RECRUITMENT PROCEDURES

Patients scheduled to undergo laparoscopic gastric bypass surgery for morbid obesity will be seen in the preop clinic by our research coordinator. Patients should have a diagnosis of obstructive sleep apnea as confirmed by sleep study and are not currently using a CPAP devise. If no sleep study is available, patients should have the 4 clinical predictors of obstructive sleep apnea as described by STOP (Snoring, Tiredness during daytime, Observed apnea, high blood Pressure) screening questionnaire. <Chung, F Anesthesiology 2008>

Patients scheduled for surgery are required to be seen in the Anesthesiology Preop Clinic. Patients scheduled for laparoscopic gastric bypass surgery will be given the opportunity to participate in this clinical trial.

#### 8.0 STUDY INTERVENTIONS/PROCEDURES

This is a prospective, randomized, double-blind, placebo-controlled single institution study. All patients will be provided written informed consent in the preop clinic prior to participation. Patients will be randomly allocated to the ketamine (K) study group or the control (C) group. Random allocation of patients will be performed by study coordinator using closed envelopes containing allocation group. All patients will be provided standard hospital care.

On the day of surgery, baseline oxygen saturation measurements will be recorded for each patient. The study coordinator will provide the attending anesthesiologist with a 30ml syringe containing either ketamine (K) 10mg/ml or saline (C). Both syringes will be labeled "Ketamine 10mg/ml" along with time and date of preparation by the pharmacy. In the operating room, standard ASA monitors will be used along with arterial and /or CVP monitoring according to the preference of the attending anesthesiologist. After adequate preoxygenation with 100% oxygen, general anesthesia will be induced with intravenous midazolam 2mg, fentanyl 100mcg and propofol, 2-3 mg/kg ideal body weight (IBW) followed by rocuronium 50mg before endotracheal intubation. IBW is calculated by the Hamwi Formula: men start with 106 lbs for first 5 feet + 6 lbs for each inch over 5 feet,

women use 100 lbs for first 5 feet + 5 lbs for each inch over 5 feet (Medium frame); for small frame (- 10%), large frame (+ 10%).

Anesthesia will be maintained in the both groups with inhaled Sevoflurane starting at 4% end-tidal concentration and titrated to keep the bispectral index (BIS) value at 40-50 (Bispectral Index, Aspect Biomedical, Natick, MA). After induction and before surgical incision is made, patients will receive an intravenous bolus saline or the study drug, S(+) ketamine 0.5mg/kg IBW bolus followed by a continuous infusion of 0.5 mg/kg/hr (IBW) using a Baxter syringe pump. The infusion will be stopped at the closure of the abdominal fascia layer, approximately 30 minutes before the end of surgery. In both groups, neuromuscular blockade will be maintained with rocuronium and titrated to train-of-four (TOF) ratio until the abdominal fascia is closed. Oxygen, air (no nitrous oxide), IV fluids, vasoactive drugs, and fentanyl (up to 5mcg/kg IBW) will be titrated at the anesthesiologist's discretion to maintain hemodynamics at 25% of baseline. Glycopyrolate and neostigmine will be given to facilitate reversal of neuromuscular blockade. Sevoflurane will be discontinued immediately prior to completion of surgery. All patients will receive IV ketorolac 30mg at conclusion of closure of abdominal fascia. Endotracheal tube will be removed when patient meets extubation criteria (spontaneous breathing with min 6ml/kg IBW tidal volume, following commands with ability to sustain hand grip and 5-sec head lift). All patients will then be discharged from the operating room to the post-anesthesia care unit (PACU).

Upon arrival in the PACU, all patients will be monitored according to standard post-anesthesia protocols for a period of at least 2 hours. The PACU nurse that is blinded to treatment group will assess and record baseline vital signs including HR, BP, RR, SpO2, and VRS score. Modified Aldrete score including presence of nausea/vomiting, sedation level or evidence of dysphoria will be recorded at 15 minute intervals. SpO2 will be monitored continuously with documentation of oxygen flow required to maintain oxygen saturation of at least 94%. As per PACU protocol, initially patients will receive oxygen 40% by open face mask, with weaning to NC or RA, maintaining SpO2 > 94%. Desaturation episodes will be scored automatically by pulse oximetry analysis software (Nellcor, NPB-290). Data evaluated will include: comparison of patient demographics, time to first analgesic, number of analgesic demands, amount of analgesic consumed in the OR and PACU, frequency of side effects, and ODI (oxygen desaturation index). ODI is defined as the number of desaturations (lower than 4% from baseline) per hour of recording, which correlates with PSGdetermined apnea/hypopnea index and can be used as an indicator of postoperative apneic episodes <Ahmad S, Anesthesia and Analgesia 2008>}. Time to first analgesia request will be recorded and pain (VRS >/= 4) will be treated with intravenous morphine 2mg. This will be repeated at 5 minutes intervals until pain score improves or patient has untoward side

effects, at which time the PACU physician should be immediately called to the patient's bedside. Further monitoring for of patients in PACU or on the floor may be indicated in some patients according to the discretion of the attending anesthesiologist and surgeon; however it is not mandatory for this study. According to Terris et al., "Significant complications [of OSA] generally emerge within 2 hours after surgery. Therefore a decision regarding the level of postoperative monitoring needed may be made with confidence during the period of time that the patient is in the recovery room" <Terris DJ, Laryngoscope 1998>.

When patients are deemed suitable for discharge from the PACU, patients will be transferred to the floor where they will receive standard hospital care and monitoring including routine vital signs continuous pulse oximetry. At 24 hrs post-op, patient vital signs, VRS, and morphine usage will be assessed along with patient satisfaction related to overall anesthesia care according to a 5-point scale (1= very unsatisfied, 2=unsatisfied, 3=equivocal, 4=satisfied, 5=very satisfied).

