#### 12.0 PATIENT SAFETY AND DATA SECURITY MONITORING

#### Assessment of Level of Risk:

This study poses a very low level of risk to the study participants. While participating in this study, the possible risks include: experiencing side effects from low dose ketamine and possible loss of confidentiality. The most common side effect, emergence delirium is unlikely using low-dose ketamine, when given with anesthetic induction agents and inhalational anesthetic gas. Multiple studies have demonstrated safety and efficacy with few if any, adverse side effects <Bell RF, Cochrane Review, 2005>.

Oversight of this investigation will be provided by primary investigator, [name]. Additional oversight will be provided by the Department of Anesthesiology Human Subjects Research Committee and its related support staff.

The mechanisms for HIPAA compliance [including a detailed electronic personal health information (PHI) data path]:

Patient privacy will be protected through participation as per HIPPA guidelines. Patient confidentiality will be protected through password protected computers within the UAB anesthesiology department. Only study investigators listed on this IRB will have access to protected patient information.

Patients will be identified as potential study participants in the during their preoperative clinic visit. Study coordinator will be contacted to provide the patient written and verbal informed consent several days prior to surgery.

Study coordinator will provide the patient written and verbal informed consent several days prior to surgery. Patient will be required to return home to read informed consent along with study background and protocol information. They will contact study coordinator if interested in participating in the study.

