- Once a potential participant has been identified (see steps outlined in item g above), then the study PI and/or the research assistant will perform a chart review to complete the Eligibility Checklist. If a patient meets the eligibility criteria, as outlined on the Eligibility Checklist, then the PI or the research assistant will meet the patient and present the details of this study to the patient. If the patient agrees to participate, then informed consent will be obtained. Eligibility determination and screening will occur in the Preoperative Assessment Clinic (PAC) in The Kirklin Clinic (TKC) and Highlands.

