# 16. Protocol Procedures, Methods, and Duration of the Study—in nontechnical language

- Participants in this study will be randomized to two groups: One group will receive an intravenous (IV) dose of ketamine during the surgery. The other group will receive a normal saline placebo IV (control group). For the patients that are randomized to the ketamine group, the PI will submit an order for the ketamine to the research pharmacist. The pharmacist will determine the dosing of ketamine based on a standard calculation and prepare the syringe that will be used to dispense the ketamine. For both groups, the IV infusion will be discontinued at the conclusion of the surgery. Participants will receive standard anesthetic drugs and appropriate pain medication to control their postoperative pain in keeping with the current practice. We will compare recovery data including vital signs and pain scores as well as potential side effects of controlled versus study group. Approximately 24 hours after surgery, a patient assessment form will be completed ("24 Hr Post-Operative Data Collection Form") by the PI or research study team.
- b. What is the probable length of time required for the entire study (i.e., recruitment through data analysis to study closure)?
  Approximately two years
- Participants will be involved during surgery, during their recovery in the PACU, and at one time point approximately 24 hours postoperatively (to complete the Post-Operative Patient Satisfaction Assessment Form).
- d. If different phases are involved, what is the duration of each phase in which the participants will be involved? If no phases are involved, enter "not applicable." Not applicable
- **e.** List the procedures, the length of time each will take, and the frequency of repetition, and indicate whether each is done solely for research or would already be performed for treatment or diagnostic purposes (routine care) for the population. *Insert additional table rows as needed.*

Procedure	Length of Time	Frequency of	Doscorrah (Dos)
rioccarc			Research (Res) -
	Required of	Repetition	OR- Routine Care
	Participants		
Pregnancy testing for women of	<5 minutes	once	□Res ⊠Routine
childbearing potential			
Weight measurement	<5 minutes	once	□Res ⊠Routine
Normal Saline or Ketamine infusion	<three hours<="" td="">once	⊠Res □Routine	</three>	once	⊠Res □Routine
Monitoring and measurement of	From onset of	Continuously	□Res ⊠Routine

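### Allocation concealment is not protected by the stated procedure: a recruiter allocates from envelopes described only as closed, and in the re-opened form the PI learns each past arm

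*Combined protocol and SAP*

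**What the plan says.** The document contains two accounts of how the trial is run: the 2009 protocol (version dated 11/16/09), and the human subjects protocol resubmitted to re-open the study (item 23).

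**2009 protocol.** Section 7.0 has randomization in its heading but describes only recruitment: candidates "will be seen in the preop clinic by our research coordinator". Section 12.0 says "Study coordinator will provide the patient written and verbal informed consent several days prior to surgery", and that interested patients then contact the coordinator. Section 8.0 says "Random allocation of patients will be performed by study coordinator using closed envelopes containing allocation group". It also says "All patients will be provided written informed consent in the preop clinic prior to participation". On the day of surgery the coordinator hands the syringe to the attending anesthesiologist. Both syringes carry the same drug label, "along with time and date of preparation by the pharmacy". The trial is described as double-blind.

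**Re-opened human subjects protocol.** Once a candidate is identified, "then the study PI and/or the research assistant will perform a chart review to complete the Eligibility Checklist" (item 15), and the PI or the research assistant presents the study. Item 20.c has a member of the research team obtain consent. Item 16 says "For the patients that are randomized to the ketamine group, the PI will submit an order for the ketamine to the research pharmacist". No matching order for saline is described. Item 15.d says that patients are randomly assigned, 150 in total, and gives no mechanism.

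Neither account states how the sequence is generated, whether it is blocked or stratified, who prepares or keeps the envelopes, when they are opened, or whether they are opaque, sealed or numbered.

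**The concern.** Randomization protects the comparison only if whoever judges and enrols a patient cannot foresee that patient's arm. Here the stated procedures weaken that separation in two ways. In the 2009 text, allocation is in the hands of someone who recruits. In the re-opened form, someone who may judge eligibility learns the arm of every patient already randomized.

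Entry leaves room for judgement. ASA class and the criteria for significant cardiovascular, respiratory, psychiatric, neurologic, hepatic or renal disease are partly discretionary (section 6.0 and item 15). If patients expected to have more pain or more desaturation entered one arm more often, opioid use, pain scores and the oxygen desaturation index would all shift. Later masking, such as the identical syringe labels and the blinded PACU nurse (section 8.0), protects assessment and not entry. Section 11.0 plans only unadjusted tests, and no analysis reliably removes selection on unmeasured prognosis.

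There is also a direct conflict over blinding. A PI who must know the arm in order to place an order is not blind, and item 16 lets the PI or study team complete the 24-hour assessment.

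**Working it through.** The documents give no figure to reproduce on this point, so the main check sets the roles side by side.

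| Step | 2009 protocol | Re-opened human subjects protocol |
|---|---|---|
| Meets candidates or presents the study | Coordinator (7.0) | PI or research assistant (item 15) |
| Decides eligibility | Not stated | PI and/or research assistant complete the checklist (item 15) |
| Consent | Coordinator (12.0) | A research team member (item 20.c) |
| Allocates | Coordinator, closed envelopes (8.0) | Not stated |
| Keeps envelopes or list | Not stated | Not stated |
| Time of allocation | Not stated | Not stated |
| Learns the arm afterwards | Not stated; identical labels | PI, through the ketamine order (item 16) |

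1. In the 2009 column one role covers contact, consent and allocation. The only barrier between that role and the assignment is that the envelope is closed.
2. In the re-opened column the PI can stand at both ends. The PI may judge eligibility, and later must know the arm to place the ketamine order. With no saline order described, the absence of an order identifies the other arm.
3. Knowing past arms does not by itself reveal the next one. Under simple randomization it carries no information about it. Under blocked randomization with a known block size, the last assignment in a block is certain once the others are known. The documents neither state nor exclude blocking, so predictability is possible but not shown.

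**Illustration of what steering would do.** Inputs:
- 32 per arm (section 11.0).
- 75 per arm, which is 150 / 2, assuming equal arms (items 15.a and 15.d give only the total).
- No true effect, and a two-sided 5% test.
- Assumed: a proportion p of allocations is steered, all in one direction, and the steered patients differ by 1 SD between arms.

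Formulas: shift = p × 1 SD; SE = √(2/n) SD; z = shift / SE; rejection rate = P(Z > 1.96 − z) + P(Z < −1.96 − z).

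| n per arm | SE (SD) | p | z | Rejection rate |
|---|---|---|---|---|
| 32 | 0.250 | 0.10 | 0.40 | 0.069 |
| 32 | 0.250 | 0.20 | 0.80 | 0.126 |
| 75 | 0.163 | 0.10 | 0.61 | 0.094 |
| 75 | 0.163 | 0.20 | 1.22 | 0.232 |

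The rate is higher at 75 per arm because a fixed bias is larger relative to a smaller standard error. Enrolling more patients does not dilute it.

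**The case against.** The best reply is that closed envelopes are a concealment method, though a thinly described one, and that consent is stated to precede participation. A reader might infer that assignments are open to the recruiter, or that staff can know or choose the next arm. The documents do not support that. They do not say that anyone sees or opens an envelope before enrolment. Custody of the envelopes is inferred from the coordinator performing the allocation, and the 2009 text does not name who decides eligibility. The patient's own call to the coordinator is also part of entry.

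Two further inferences fail. Handing over the syringe does not disclose the next arm: the labels match, and delivery comes days after consent. Nor do the documents show that patients are allocated before the day-of-surgery oxygen saturation is known. That reading rests on the order of sentences in section 8.0, which fixes no time for allocation. It would in any case be a question of exclusion after randomization.

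Several entry criteria are objective (age, creatinine, oxygen saturation, pregnancy test), which limits the room for steering without removing it. The Drug Review Sheet is named as an attachment and is not part of the document; it might describe dispensing.

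What does not yield is the text itself. Section 8.0 gives allocation to a recruiter. Item 16 gives the PI the arm. The re-opened form describes no concealment method at all.

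**Conclusion.** The point stands as one of unprotected concealment, not of demonstrated foreknowledge. It is more than missing detail, because the procedures as written place allocation with a recruiter and disclose past arms to a PI who may screen. The second of these contradicts the double-blind description, whatever the randomization scheme. The risk to entry from the PI's knowledge depends on restricted randomization, which is unknown.

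The procedure governs every allocation, whether 65 (section 6.0) or 150 (item 15.a). The resulting bias cannot be estimated from the documents. A reader might take the 7% to 23% false-positive rates as the trial's actual error rate. They are not: the steering proportions, the single direction and the 1 SD difference are all assumptions, and the conclusion does not depend on them.

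**What to change.** Replace the envelope sentence in section 8.0 and the ordering sentence in item 16 with one procedure:

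- The research pharmacy, which both accounts already use, or another person outside recruitment, holds a computer-generated sequence. State the method of generation and any blocking in a document that recruiters do not see.
- The next entry is assigned by subject number only after consent and eligibility are recorded.
- One common, arm-neutral order is placed for every patient, and the pharmacy issues identically labelled, numbered syringes for both arms.
- Recruiters and the PI see neither list nor envelopes.

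If envelopes are kept, they should be opaque, sealed and sequentially numbered, held by someone outside recruitment, and opened only after enrolment is recorded. This would serve for concealment, but the order in item 16 still has to become arm-neutral.

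Reconcile the roles in sections 7.0, 8.0 and 12.0 with items 15, 16 and 20.c, so that one account says who screens, consents, assigns and dispenses.

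The cost is protocol wording, some list-keeping by the pharmacy, and syringe preparation timed after eligibility is confirmed. No extra patient visit is needed. Whether the pharmacy can absorb the work with its present staff is not stated and should be asked.

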#### 4.0 OBJECTIVE(S) & HYPOTHESIS

Obstructive sleep apnea (OSA) has been estimated to affect between 2 and 4% of the U.S. population < Young T, NEJM 1993>. It is a serious, lifethreatening condition associated with obesity, hypertension, congestive heart failure, pulmonary hypertension, coronary artery disease, and cardiac arrhythmias and has an 8 year mortality rate of nearly 40% <Parrish JM, Mayo Clin Proc 2004, He J, Chest 1988>. Following general anesthesia, patients with OSA have been noted to have a significantly increased risk of respiratory complications, morbidity and mortality <Gupta RM Mayo Clin Proc 2001, Liao P, Sleep 2007, Young T, Sleep 2007, Marshall NS, Sleep 2008 >. This may be due to residual effects of inhaled anesthetics which can decrease upper pharyngeal muscle tone leading to airway compromise in OSA patients <Bell RL, Anes Clin of NA 2005>. Also, OSA patients are exquisitely sensitive to the ventilatory depressant effects of postoperative opioids, causing decreased responsiveness to hypercarbia and episodic arterial hypoxemia <Ostermeier AM, Anes Anal 1997, Stoelting, Anesthesia and Coexisting Disease 4th ed>. Currently, there is not a well-established, general anesthetic technique that will decrease the risk of complications in OSA patients. The objective of this study is to compare the postoperative recovery profile of OSA patients receiving

standard Sevoflurane inhaled anesthesia versus Sevoflurane combined with a low-dose ketamine infusion.

We hypothesize that the group of obstructive sleep apnea patients that receive low-dose intraoperative ketamine will report lower pain scores, require less supplemental intravenous Morphine, and have less frequent side effects and desaturation episodes post-operatively than the group receiving saline.

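### The plan fixes recorded pain scores only at PACU arrival and 24 hours, and does not say which one the VRS test uses

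*Combined protocol and SAP*

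**What the plan says.** Section 4.0 of the combined protocol and SAP expects that ketamine patients "will report lower pain scores, require less supplemental intravenous Morphine", followed by fewer side effects and desaturations. Pain is named first, but no outcome is labelled primary. The sample size in Sections 5.0 and 11.0 rests on opioid requirement.

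Section 8.0 sets the measurements:

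- **PACU arrival.** A blinded nurse "will assess and record baseline vital signs including HR, BP, RR, SpO2, and VRS score".
- **During the PACU stay.** "Modified Aldrete score including presence of nausea/vomiting, sedation level or evidence of dysphoria will be recorded at 15 minute intervals". Pain is not among the items.
- **Length of stay.** "all patients will be monitored according to standard post-anesthesia protocols for a period of at least 2 hours".
- **Rescue.** "pain (VRS >/= 4) will be treated with intravenous morphine 2mg", and "This will be repeated at 5 minutes intervals until pain score improves" or side effects intervene.
- **Next day.** "At 24 hrs post-op, patient vital signs, VRS, and morphine usage will be assessed".

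The list of data to be evaluated in Section 8.0 does not include VRS. Sections 5.0 and 11.0 nevertheless assign VRS to a Mann-Whitney U-test, without a time point, a summary measure or a rule for repeated readings. Item 16 of the human subjects protocol form says pain scores will be compared and describes 24-hour forms, but adds no PACU times.

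**The concern.** Section 3.0 looks for the benefit of ketamine in the PACU recovery profile. To compare pain over that period, both arms need scores taken at the same times whatever treatment the patient received. The plan has such scores at arrival and again about a day later, with none fixed in between.

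If the analyst uses only the fixed readings, most of the PACU period is not represented. If the analyst adds whatever pain scores were charted around morphine, the number of readings per patient depends on how much rescue that patient needed. The hypothesis expects ketamine to change exactly that. Because no time point is named, the choice could also be made after the data are seen. Scores that were not taken during the stay cannot be recovered later.

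**Working it through.** **1. The plan's own figure.** The only sample-size figure is 32 per group, for a decrease of more than 30% in opioid requirement (80% power, 5% type 1 error). With n = 2(z_α + z_β)²(SD/Δ)², the detectable standardised difference at n = 32 is:

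- two-sided: (1.96 + 0.84) × √(2/32) = 0.70, so SD/control mean = 0.30/0.70 ≈ 0.43;
- one-sided: (1.645 + 0.84) × √(2/32) = 0.62, so SD/control mean = 0.30/0.62 ≈ 0.48.

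The documents give no SD or control mean, and do not say whether the test is one- or two-sided. The 32 can therefore be back-solved but not verified. It says nothing about power for VRS.

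**2. Scheduled readings in the 2-hour minimum stay (Section 8.0).**

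| Item | Fixed times | Count |
|---|---|---|
| Modified Aldrete, nausea/vomiting, sedation, dysphoria | 0, 15, ..., 120 min | 120/15 + 1 = 9 |
| VRS | arrival | 1 |

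The count of 9 takes the first assessment as being at arrival. Adding the 24-hour reading gives 2 fixed VRS readings in the whole trial.

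**3. Unequal sampling if rescue-driven scores were pooled.** This example is hypothetical. Suppose a patient gets four morphine doses, at 0, 5, 10 and 15 minutes, with a score before each and one at 20 minutes. That patient contributes 5 scores in 20 minutes. A patient who is never treated contributes 1 fixed PACU score. A pooled comparison would weight the first patient 5 to 1. The documents do not say that such scores will be charted or analysed. The example shows only what the unspecified test would permit.

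**4. What a scheduled summary could gain.** For the mean of 9 equally spaced readings with common variance and within-patient correlation ρ, the variance relative to one reading is (1 + 8ρ)/9. The detectable difference at 32 per group (two-sided 5%, 80% power, normal approximation) is 0.70 × √[(1 + 8ρ)/9], in single-reading SDs. The documents give no ρ, so a range is shown.

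| Assumed ρ | Variance ratio | Detectable difference |
|---|---|---|
| one reading | 1.00 | 0.70 |
| 0.3 | 0.38 | 0.43 |
| 0.5 | 0.56 | 0.52 |
| 0.7 | 0.73 | 0.60 |
| 0.9 | 0.91 | 0.67 |

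The human subjects protocol form gives 150 participants rather than 65. That would change the absolute differences but not the variance ratios, which do not depend on n. The table covers precision only. It takes no account of morphine titration shrinking the true difference in VRS.

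**The case against.** The strongest defence is that more pain checks will occur than the two that are written down. Section 8.0 invokes standard post-anaesthesia monitoring and calls the arrival set a baseline, which suggests later readings. A rescue trigger at VRS 4 also cannot operate unless someone asks about pain. This stands, and it rules out one tempting inference, that an untreated patient has no pain score between arrival and 24 hours. The documents support only that none is scheduled or stated to be recorded. They do not show common times that an analyst could use.

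Three other inferences also go too far:

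- *Pain is the lead hypothesis.* It is listed first, but no primary outcome is named and the powered outcome is opioid use.
- *The arrival score is confounded by emergence.* Allocation is random and the nurse is blinded, so emergence may add noise or form part of the treatment effect, but it does not confound the comparison. Patients must also be following commands before extubation.
- *Time to first analgesic is compromised.* Section 8.0 records it as the time of the patient's request, which needs no scheduled VRS.

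Two objections to the remedy have weight. Morphine is titrated against VRS in both arms, so average PACU scores are pulled together and a real analgesic effect may appear mainly as lower morphine use. Extra VRS checks also create more occasions on which the existing trigger may be met. The first calls for joint interpretation with morphine. The second is small and applies equally to both arms.

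**Conclusion.** The concern holds as a gap in scheduling and analysis. After PACU arrival there is no common scheduled VRS until 24 hours, and the planned Mann-Whitney test does not say which reading it uses. Over the minimum stay the plan has 1 fixed VRS against 9 fixed Aldrete and side-effect assessments.

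The statistical size of the gap depends on the within-patient correlation. Across an assumed 0.3 to 0.9, averaging nine scheduled readings lowers the detectable difference from 0.70 to between 0.43 and 0.67 single-reading SDs, so the gain could be substantial or slight. The firmer benefit is equal sampling of both arms. No bias in a result has been shown, because the documents do not commit to pooling rescue-driven scores. The change is worth making before enrolment, but it does not bear on the powered opioid comparison.

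**What to change.** In Section 8.0, add VRS to the items recorded at each 15-minute PACU assessment, in both arms, for at least the first 2 hours.

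In Sections 5.0 and 11.0:

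- name the PACU pain measure, for example each patient's mean of the scheduled VRS readings over 0-120 minutes, compared by the Mann-Whitney test already planned;
- state that only scheduled readings enter it, so scores taken around rescue stay out;
- report arrival VRS and 24-hour VRS separately;
- state that PACU VRS will be interpreted alongside PACU morphine use, because titration to VRS draws the scores together in both arms.

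The cost is one more line on the PACU sheet, filled in by the same blinded nurse at times already set, plus slightly more occasions, equal in both arms, for the existing VRS trigger to be met. The rescue rule itself is not altered.
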